14.3 Safety Data

14.3.1 Displays of Adverse Events

Table 117: Overall Summary of Adverse Events- Safety Population*[‡]

	Group 1 Fluzone (N=X)		Group 2 Fluzone + AF03 (N=X)		Group 3 Fluzone + Advax-CpG (N=X)		Group 4 Flublok (N=X)		Group 5 Flublok + AF03 (N=X)		Group 6 Flublok + Advax-CpG (N=X)		All Subjects (N=X)	
	n	%	n	%	n	%	n	%	n	%	n	%	n	%
Subjects ^a with														
At least one local solicited adverse event	x	x	x	x	x	x	x	x	x	x	x	x	x	x
At least one grade 3 local solicited adverse event	x	x	x	x	x	x	x	x	x	x	x	x	x	x
At least one systemic solicited adverse event	x	x	x	x	x	x	x	x	x	x	x	x	x	x
At least one grade 3 systemic solicited adverse event	x	x	x	x	x	x	x	x	x	x	x	x	x	x
At least one unsolicited adverse event	x	x	x	x	x	x	x	x	x	x	x	x	x	x
At least one related unsolicited adverse event	x	x	x	x	x	x	x	x	x	x	x	x	x	x
Mild (Grade 1)	x	x	x	x	x	x	x	x	x	x	x	x	x	x
Moderate (Grade 2)	x	x	x	x	x	x	x	x	x	x	x	x	x	x
Severe (Grade 3)	x	x	x	x	x	x	x	x	x	x	x	x	x	x
Not yet assessed														
At least one severe (Grade 3) unsolicited adverse event	x	x	x	x	x	x	x	x	x	x	x	x	x	x
Related	x	x	x	x	x	x	x	x	x	x	x	x	x	x
Unrelated	x	x	x	x	x	x	x	x	x	x	x	x	x	x

	Group 1 Fluzone (N=X)		Group 2 Fluzone + AF03 (N=X)		Group 3 Fluzone + Advax-CpG (N=X)		Group 4 Flublok (N=X)		Group 5 Flublok + AF03 (N=X)		Group 6 Flublok + Advax-CpG (N=X)		All Subjects (N=X)	
	n	%	n	%	n	%	n	%	n	%	n	%	n	%
Subjects ^a with	x	x	x	x	x	x	x	x	x	x	x	x	x	x
At least one serious adverse event ^b	x	x	x	x	x	x	x	x	x	x	x	x	x	x
At least one related, serious adverse event	x	x	x	x	x	x	x	x	x	x	x	x	x	x
At least one adverse event leading to early termination ^c	x	x	x	x	x	x	x	x	x	x	x	x	x	x
At least one medically attended adverse event	x	x	x	x	x	x	x	x	x	x	x	x	x	x
At least one adverse event of special interest	x	x	x	x	x	x	x	x	x	x	x	x	x	x
At least one new onset chronic medical condition	x	x	x	x	x	x	x	x	x	x	x	x	x	x
At least one potentially immune mediated medical condition	x	x	x	x	x	x	x	x	x	x	x	x	x	x
At least one abnormal clinical safety laboratory adverse event	x	x	x	x	x	x	x	x	x	x	x	x	x	x
Mild (Grade 1)	x	x	x	x	x	x	x	x	x	x	x	x	x	x
Moderate (Grade 2)	x	x	x	x	x	x	x	x	x	x	x	x	x	x
Severe (Grade 3)	x	x	x	x	x	x	x	x	x	x	x	x	x	x
N = Number of subjects in the Safety Population														
^a Subjects are counted once for each category regardless of the number of events.														
^b A listing of Serious Adverse Events is included in Tab AE SAE Listing.														
^c As reported on the Adverse Event eCRF.														

Table 118: Adverse Events Occurring in 5% of Subjects in Any Study Arm by MedDRA System Organ Class and Preferred Term, and Study Arm - Safety Population

Preferred Term	MedDRA System Organ Class	Group 1 Fluzone (N=X)			Group 2 Fluzone + AF03 (N=X)			Group 3 Fluzone + Advax-CpG (N=X)			Group 4 Flublok (N=X)			Group 5 Flublok + AF03 (N=X)			Group 6 Flublok + Advax-CpG (N=X)			All Subjects (N=X)		
		n	%	Events	n	%	Events	n	%	Events												
Serious Adverse Events																						
All	All	x	x	x	x	x	x	x	x	x	x	x	x	x	x	x	x	x	x	x	x	x
PT1	SOC1	x	x	x	x	x	x	x	x	x	x	x	x	x	x	x	x	x	x	x	x	x
Etc.	Etc.																					
Other (Non-serious) Adverse Events																						
All	All	x	x	x	x	x	x	x	x	x	x	x	x	x	x	x	x	x	x	x	x	x
PT1	SOC1	x	x	x	x	x	x	x	x	x	x	x	x	x	x	x	x	x	x	x	x	x
Etc	Etc																					
N = Number of subjects in the Safety Population (number of subjects at risk). n = Number of subjects reporting event. Events= total frequency of events reported.																						

14.3.1.1 Solicited Adverse Events

Table 119: Number and Percentage of Subjects Experiencing Solicited Events with 95% Confidence Intervals by Symptom and Study Arm – Safety Population

Symptom	Group 1 Fluzone (N=X)			Group 2 Fluzone + AF03 (N=X)			Group 3 Fluzone + Advax-CpG (N=X)			Group 4 Flublok (N=X)			Group 5 Flublok + AF03 (N=X)			Group 6 Flublok + Advax-CpG (N=X)		
	n	%	95% CI	n	%	95% CI	n	%	95% CI	n	%	95% CI	n	%	95% CI	n	%	95% CI
Any Symptom	x	xx	x.x, x.x	x	xx	x.x, x.x	x	xx	x.x, x.x	x	xx	x.x, x.x	x	xx	x.x, x.x	x	xx	x.x, x.x
Any Systemic Symptom																		
Fever																		
Feverishness																		
Fatigue																		
Malaise																		
Myalgia																		
Arthralgia																		
Headache																		
Nausea																		
Any Local Symptom																		
Pain																		
Tenderness																		
Pruritus																		
Ecchymosis																		
Ecchymosis (measurement)																		
Erythema																		
Erythema (measurement)																		
Induration/Swelling																		

Symptom	Group 1 Fluzone (N=X)			Group 2 Fluzone + AF03 (N=X)			Group 3 Fluzone + Advax-CpG (N=X)			Group 4 Flublok (N=X)			Group 5 Flublok + AF03 (N=X)			Group 6 Flublok + Advax-CpG (N=X)		
	n	%	95% CI	n	%	95% CI	n	%	95% CI	n	%	95% CI	n	%	95% CI	n	%	95% CI
Induration/Swelling (measurement)																		
N = Number of subjects in the Safety Population who received any study vaccination. 95% CI estimated using Clopper-Pearson exact method																		

Table 120: Logistic Regression Model to Evaluate the Relationship of Treatment with Reporting Any Local Event Post First Study Vaccination - Safety Population

Model Parameter	Parameter Category	Parameter Estimate	SE	p-value	Odds Ratio	95%CI
Intercept	N/A	xxx.x	xxx.x	x.xxx	-	-
Treatment	Fluzone	-	-	-	-	-
	Fluzone + AF03	xxx.x	xxx.x	x.xxx	xx.x	xx.x-xx.x
	Fluzone + Advax-CpG	xxx.x	xxx.x	x.xxx	xx.x	xx.x-xx.x
	Flublok	xxx.x	xxx.x	x.xxx	xx.x	xx.x-xx.x
	Flublok + AF03	xxx.x	xxx.x	x.xxx	xx.x	xx.x-xx.x
	Flublok + Advax-CpG	xxx.x	xxx.x	x.xxx	xx.x	xx.x-xx.x

N = Number of subjects in the safety population.

Table with similar format:

Table 121: Logistic Regression Model to Evaluate the Relationship of Treatment with Reporting Any Systemic Event Post First Study Vaccination - Safety Population

Table 122: Number and Percentage of Subjects Experiencing Solicited Events by Symptom, Maximum Severity and Study Arm Post First Study Vaccination – Safety Population*

Symptom	Severity	Group 1 Fluzone (N=X)		Group 2 Fluzone + AF03 (N=X)		Group 3 Fluzone + Advax-CpG (N=X)		Group 4 Flublok (N=X)		Group 5 Flublok + AF03 (N=X)		Group 6 Flublok + Advax-CpG (N=X)	
		n	% (95% CI)	n	% (95% CI)	n	% (95% CI)	n	% (95% CI)	n	% (95% CI)	n	% (95% CI)
Any Symptom	None	x	xx (xx-xx)	x	xx (xx-xx)	x	xx (xx-xx)	x	xx (xx-xx)	x	xx (xx-xx)	x	xx (xx-xx)
	Mild												
	Moderate												
	Severe												
Any Systemic Symptom	None	x	xx (xx-xx)	x	xx (xx-xx)	x	xx (xx-xx)	x	xx (xx-xx)	x	xx (xx-xx)	x	xx (xx-xx)
	Mild												
	Moderate												
	Severe												
Fever	None												
	Mild												
	Moderate												
	Severe												
Feverishness	None												
	Mild												
	Moderate												
	Severe												
Fatigue	None												
	Mild												
	Moderate												
	Severe												
Malaise	None												

Symptom	Severity	Group 1 Fluzone (N=X)		Group 2 Fluzone + AF03 (N=X)		Group 3 Fluzone + Advax-CpG (N=X)		Group 4 Flublok (N=X)		Group 5 Flublok + AF03 (N=X)		Group 6 Flublok + Advax-CpG (N=X)	
		n	% (95% CI)	n	% (95% CI)	n	% (95% CI)	n	% (95% CI)	n	% (95% CI)	n	% (95% CI)
	Mild												
	Moderate												
	Severe												
Myalgia	None												
	Mild												
	Moderate												
	Severe												
Arthralgia	None												
	Mild												
	Moderate												
	Severe												
Headache	None												
	Mild												
	Moderate												
	Severe												
Nausea	None												
	Mild												
	Moderate												
	Severe												
Any Local Symptom	None												
	Mild												
	Moderate												
	Severe												

Symptom	Severity	Group 1 Fluzone (N=X)		Group 2 Fluzone + AF03 (N=X)		Group 3 Fluzone + Advax-CpG (N=X)		Group 4 Flublok (N=X)		Group 5 Flublok + AF03 (N=X)		Group 6 Flublok + Advax-CpG (N=X)	
		n	% (95% CI)	n	% (95% CI)	n	% (95% CI)	n	% (95% CI)	n	% (95% CI)	n	% (95% CI)
Pain	None												
	Mild												
	Moderate												
	Severe												
Tenderness	None												
	Mild												
	Moderate												
	Severe												
Pruritus	None												
	Mild												
	Moderate												
	Severe												
Ecchymosis	None												
	Mild												
	Moderate												
	Severe												
Ecchymosis (measurement)	None												
	Mild												
	Moderate												
	Severe												
Erythema	None												
	Mild												

Symptom	Severity	Group 1 Fluzone (N=X)		Group 2 Fluzone + AF03 (N=X)		Group 3 Fluzone + Advax-CpG (N=X)		Group 4 Flublok (N=X)		Group 5 Flublok + AF03 (N=X)		Group 6 Flublok + Advax-CpG (N=X)	
		n	% (95% CI)	n	% (95% CI)	n	% (95% CI)	n	% (95% CI)	n	% (95% CI)	n	% (95% CI)
	Moderate												
	Severe												
Erythema (measurement)	None												
	Mild												
	Moderate												
	Severe												
Induration/Swelling	None												
	Mild												
	Moderate												
	Severe												
Induration/Swelling (measurement)	None												
	Mild												
	Moderate												
	Severe												

N = Number of subjects in the Safety Population.
 95% CI estimated using Clopper-Pearson exact method.
 Severity is the maximum severity reported over all solicited symptoms post dosing for each subject.

Table 123: Number and Percentage of Subjects Experiencing Solicited Events by Symptom, Severity, Day Post Dose, and Study Arm Post First Study Vaccination - Safety Population

Symptom	Severity	Pre-Vac		Post-Vac		Day 1		Day 2		Day 3		Day 4		Day 5		Day 6		Day 7		Day 8+	
		n	%	n	%	n	%	n	%	n	%	n	%	n	%	n	%	n	%	n	%
Group 1: Fluzone (N=X)																					
Any Symptom	None																				
	Mild																				
	Moderate																				
	Severe																				
Any Systemic Symptom	None																				
	Mild																				
	Moderate																				
	Severe																				
Fever	None																				
	Mild																				
	Moderate																				
	Severe																				
Feverishness	None																				
	Mild																				
	Moderate																				
	Severe																				
Fatigue	None																				
	Mild																				
	Moderate																				
	Severe																				
Malaise	None																				

Symptom	Severity	Pre-Vac		Post-Vac		Day 1		Day 2		Day 3		Day 4		Day 5		Day 6		Day 7		Day 8+	
		n	%	n	%	n	%	n	%	n	%	n	%	n	%	n	%	n	%	n	%
	Mild																				
	Moderate																				
	Severe																				
Myalgia	None																				
	Mild																				
	Moderate																				
	Severe																				
Arthralgia	None																				
	Mild																				
	Moderate																				
	Severe																				
Headache	None																				
	Mild																				
	Moderate																				
	Severe																				
Nausea	None																				
	Mild																				
	Moderate																				
	Severe																				
Any Local Symptom	None																				
	Mild																				
	Moderate																				
	Severe																				
Pain	None																				
	Mild																				

Symptom	Severity	Pre-Vac		Post-Vac		Day 1		Day 2		Day 3		Day 4		Day 5		Day 6		Day 7		Day 8+		
		n	%	n	%	n	%	n	%	n	%	n	%	n	%	n	%	n	%	n	%	
	Moderate																					
	Severe																					
Tenderness	None																					
	Mild																					
	Moderate																					
	Severe																					
Pruritus	None																					
	Mild																					
	Moderate																					
	Severe																					
Ecchymosis	None																					
	Mild																					
	Moderate																					
	Severe																					
Ecchymosis (measurement)	None																					
	Mild																					
	Moderate																					
	Severe																					
Erythema	None																					
	Mild																					
	Moderate																					
	Severe																					
Erythema (measurement)	None																					
	Mild																					
	Moderate																					

Symptom	Severity	Pre-Vac		Post-Vac		Day 1		Day 2		Day 3		Day 4		Day 5		Day 6		Day 7		Day 8+	
		n	%	n	%	n	%	n	%	n	%	n	%	n	%	n	%	n	%	n	%
	Severe																				
Induration/Swelling	None																				
	Mild																				
	Moderate																				
	Severe																				
Induration/Swelling (measurement)	None																				
	Mild																				
	Moderate																				
	Severe																				

[Repeat for all study arms]

N = Number of subjects in the Safety Analysis Population. Severity is the maximum severity reported post vaccination for each subject for each day.

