**Table 1: Study Objectives and Outcome Measures**

Primary Safety Objectives	Primary Safety Outcome Measures

 
To assess the safety and reactogenicity of 2018/2019 Fluzone and Flublok with and without AF03 or Advax-CpG55.2 adjuvant.
 
	
 
Occurrence of solicited injection site and systemic reactogenicity events through approximately Day 8 after the first study vaccination.
 
Occurrence of unsolicited adverse events from the time of the first study vaccination through approximately Day 29.
 
Occurrence of all SAEs through approximately 12 months following receipt of the first study vaccination.
 
Occurrence of abnormal clinical safety laboratory AEs from the time of study vaccination through approximately Day 8 after the first study vaccination.
 

Primary Immunogenicity Objectives	Primary Immunogenicity Outcome Measures

 
To assess the serum hemagglutination inhibition (HAI) antibody responses against 2018/2019 QIV strains from baseline (Day 1) to approximately Day 29 after receipt of 2018/2019 Fluzone and Flublok with and without AF03 or Advax-CpG55.2 adjuvant.
 
	
 
The percentage of subjects achieving HAI titer seroconversion against the 2018/2019 QIV strains (defined as either a pre-vaccination titer <1:10 and a post-vaccination titer ≥1:40 or a pre-vaccination titer ≥1:10 and a minimum four-fold rise in post-vaccination antibody titer) on approximately Day 29 for each study group.
 
The percentage of subjects with an HAI titer ≥1:40 against the 2018/2019 QIV strains at baseline and approximately Day 29 for each study group.
 
Geometric mean titers (GMTs) of serum HAI against the 2018/2019 QIV strains at baseline and approximately Day 29 for each study group.
 

	
 
• Ratio of GMTs of serum HAI against the 2018/2019 QIV strains between adjuvanted and unadjuvanted study groups at baseline and approximately Day 29.
 
• Geometric mean fold rise (GMFR) in HAI titers from baseline (Day 1) against the 2018/2019 QIV strains at approximately Day 29 for each study group
 

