#### Fluzone and Flublok Vaccines

The 2018/2019 and 2019/2020 QIV products used in this study are approved by the FDA for active immunization against disease caused by influenza viruses contained in the vaccine.

Occasionally, adult recipients of unadjuvanted licensed, inactivated influenza vaccines (IIVs) may develop influenza-like reactions, such as fever, feverishness, fatigue, malaise, myalgia, arthralgia, headache, and/or nausea. Some subjects may develop reactions at the injection site, including pruritus, ecchymosis, erythema, induration, edema, pain, and/or tenderness. Most of these reactions peak in intensity in the first 24 hours after vaccination and disappear without treatment within 1 or 2 days. Analgesics (e.g., acetaminophen, ibuprofen or similar non-steroidal anti-inflammatory drugs (NSAIDs) and rest may generally relieve or lessen these reactions. Bruising can sometimes occur due to the vaccination procedure.

During the clinical development of Flublok, which is a recombinant influenza vaccine (RIV), both local and systemic reactogenicity symptoms were generally similar in frequency and severity to those observed with the active control vaccines (trivalent or quadrivalent influenza vaccines, TIV or QIV) in adults. The only SAEs that were considered related or possibly related to Flublok in any of the trials were one case of vasovagal syncope (quadrivalent RIV, within 20 minutes post-vaccination, attributed to the injection process rather than the vaccine material) and one case of non-infectious pericardial effusion (trivalent RIV, 11 days post-vaccination).

Serious immediate reactions, such as hypersensitivity, or delayed reactions, such as Guillain-Barré syndrome, have not been observed in the clinical trials with any formulations of rHA vaccines.

In addition, post-marketing surveillance of the seasonal IIVs indicates autoimmune and other disorders as potential risks; these may also include, but are not limited to, neuritis, convulsions, severe allergic reactions, syncope, encephalitis, thrombocytopenia, vasculitis, and Guillain-Barré syndrome (GBS). Reports of these reactions were rare; however, exact incidence rates cannot be precisely calculated.

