### **11.6.2 Safety Data**

Summaries and analysis of safety data will be presented for the Safety Analysis Population. All summaries and analyses will be presented for all subjects.

Solicited AEs will be summarized by severity after the first study vaccination (1-7 days post study vaccination) and as the maximum severity over all 8 days. Additionally, solicited AEs will be analyzed by taking the most severe response over the follow-up period, dichotomizing into a binary variable (none versus mild, moderate, or severe) and using standard techniques, such as exact confidence intervals, to summarize the proportion of subjects reporting each symptom, any injection site symptom, and any systemic symptom. Summaries of solicited AEs will be presented for the first study vaccination by treatment arm. The proportion of subjects reporting symptoms may be compared between treatment arms using Chi-square or Fisher's exact test. Unsolicited AEs will be coded by Medical Dictionary for Regulatory Activities (MedDRA®) for preferred term and system organ class (SOC). The numbers of SAEs and AESIs (including Protocol Specified AESIs, MAAEs, NOCMCs and PIMMCs) are likely to be small in this trial and will be reported by detailed listings showing the event description, MedDRA® preferred term and SOC, relevant dates (study vaccinations and AEs), severity, relatedness, and outcome for each event. Non-serious unsolicited AEs will be summarized as number and percentage of subjects reporting at least one event in each MedDRA® preferred term and SOC, cross tabulated by severity and relationship to study product. Additionally, the proportion of subjects and exact 95% confidence intervals of AEs in aggregate and by MedDRA® categories will be computed. Clinical laboratory data will be summarized by severity for each visit and as the maximum over all post-study vaccination visits. Graphical presentations may include box plots.

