9.3.1. Solicited Events and Symptoms

Systemic solicited adverse events were collected pre-vaccination, and systemic and local solicited adverse events were collected at-least 20 minutes post-vaccination and then daily for 7 days after the first study vaccination and graded on a scale of 0 (none), 1 (mild), 2 (moderate) and 3 (severe). Systemic events include fever, feverishness, fatigue, malaise, myalgia, arthralgia, headache, and nausea. Local events include pruritus, ecchymosis, erythema, induration/swelling, pain, and tenderness. Ecchymosis, erythema, and induration are measured by both functional and measurement grading scales as defined in [Table 7](#). The grading scale for systemic events, including quantitative grading for fever, is included in [Table 8](#).

When calculating the incidence of solicited events, each subject will be counted once at the highest severity following the applicable vaccination, and any repetitions will be ignored. For summaries presented for the first study vaccination, the denominator for percentages will be the number of subjects who received the first study vaccination with non-missing data for the event summarized.

The number and percentage of subjects reporting at least one solicited adverse event of each severity will be summarized for each solicited symptom, any systemic symptom, any local symptom, and any symptoms. For each event the denominator is the number of subjects who received the first study vaccination with non-missing data for the specific event. The 95% CI calculated using Clopper-Pearson methodology from a binomial distribution (SAS Proc Freq with a binomial option) will be presented ([Table 119](#)). Logistic regression models will be fit to estimate the effect of study arm on the probability of reporting any local event or reporting any systemic event ([Table 120](#), [Table 121](#)). If statistically significant effects are observed in the model for local events or systemic events, then additional models may be fit for each individual event of that type.

$$\text{logit}[P(\text{Event})] = \beta_0 + \beta_1 \times \text{Treatment} + \varepsilon,$$

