12. SUMMARY OF CHANGES IN THE CONDUCT OF THE STUDY OR PLANNED ANALYSES

This SAP includes one change from the analyses described in the protocol. Logistic regression will be used instead of the Chi-Square or Fisher's exact test to model the relationship of treatment with reporting any local or systemic events post vaccination. Besides providing the strength of the association between the treatment and probability of reporting any local or systemic event in terms of odds ratio, logistic regression also provides a prediction model for the probability of a local or solicited event occurring given the subject's study arm. Version 3.0 of the SAP includes moving Day 180 and Day 365 immunogenicity endpoints from secondary to exploratory endpoints and the addition of a topline report.

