GMFR (95% CI)	xx.x (xx.x,xx.x)	xx.x (xx.x,xx.x)	xx.x (xx.x,xx.x)	xx.x (xx.x,xx.x)	xx.x (xx.x,xx.x)	xx.x (xx.x,xx.x)
Day 365 Post Vaccination 1						
n	x	x	x	x	x	x
GMT (95% CI)	xxx.x (xxx.x,xxx.x)	xxx.x (xxx.x,xxx.x)	xxx.x (xxx.x,xxx.x)	xxx.x (xxx.x,xxx.x)	xxx.x (xxx.x,xxx.x)	xxx.x (xxx.x,xxx.x)
Ratio of GMTs (95% CI) ^a	-	xx.x (xx.x,xx.x)	xx.x (xx.x,xx.x)	-	xx.x (xx.x,xx.x)	xx.x (xx.x,xx.x)
Seroconversion - % (95% CI)	xx (xx, xx)	xx (xx, xx)	xx (xx, xx)	xx (xx, xx)	xx (xx, xx)	xx (xx, xx)
Titer ≥ 1:40 - % (95% CI)	xx (xx, xx)	xx (xx, xx)	xx (xx, xx)	xx (xx, xx)	xx (xx, xx)	xx (xx, xx)
GMFR (95% CI)	xx.x (xx.x,xx.x)	xx.x (xx.x,xx.x)	xx.x (xx.x,xx.x)	xx.x (xx.x,xx.x)	xx.x (xx.x,xx.x)	xx.x (xx.x,xx.x)

N = Number of subjects in the Modified Intent-to-Treat Population; n = Number of subjects with available results; GMT = Geometric Mean Titer; GMFR = Geometric Mean Fold Rise.

^aRatio of GMTs is defined as the ratio of the GMT from the adjuvanted group divided by the GMT from the corresponding unadjuvanted group. Confidence intervals for the ratio of GMTs will use the Delta Method.

Tables with similar format

- Table 22:** Summaries of Hemagglutination Inhibition Antibody Against 2018/2019 QIV Strain A/Singapore/INFIMH-16-0019/2016 IVR-186 (H3N2) by Study Day and Study Arm, Modified Intent-to-Treat Population ^{*¥}
- Table 23:** Summaries of Hemagglutination Inhibition Antibody Against 2018/2019 QIV Strain B/Phuket/3073/2013 (B Yamagata lineage) by Study Day and Study Arm, Modified Intent-to-Treat Population ^{*¥}
- Table 24:** Summaries of Hemagglutination Inhibition Antibody Against 2018/2019 QIV Strain B/Maryland/15/2016 BX-69A (B Victoria lineage) by Study Day and Study Arm, Modified Intent-to-Treat Population ^{*¥}
- Table 25:** Summaries of Hemagglutination Inhibition Antibody Against 2018/2019 QIV Strain A/Michigan/45/2015 X-275 (H1N1) by Study Day and Study Arm, Per Protocol Population ^{*¥}
- Table 26:** Summaries of Hemagglutination Inhibition Antibody Against 2018/2019 QIV Strain A/Singapore/INFIMH-16-0019/2016 IVR-186 (H3N2) by Study Day and Study Arm, Per Protocol Population ^{*¥}
- Table 27:** Summaries of Hemagglutination Inhibition Antibody Against 2018/2019 QIV Strain B/Phuket/3073/2013 (B Yamagata lineage) by Study Day and Study Arm, Per Protocol Population ^{*¥}

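### In SAP Tables 120 and 121 every odds ratio is against unadjuvanted Fluzone, so the adjuvant effect within Flublok is never printed

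*SAP*

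**What the plan says.** SAP 9.3.1 states that "Logistic regression models will be fit to estimate the effect of study arm on the probability of reporting any local event", and likewise for any systemic event. The model has an intercept and a single treatment term. The section names no reference arm and no pairwise contrasts. It adds that "If statistically significant effects are observed in the model for local events or systemic events, then additional models may be fit". These would be separate models, one per symptom, and they have no table shell.

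The shell for Table 120 (SAP Appendix 1, section 14.3.1.1), titled "Logistic Regression Model to Evaluate the Relationship of Treatment with Reporting Any Local Event Post First Study Vaccination", lists six treatment categories. The Fluzone row holds only dashes. Each of the other five arms, including Flublok alone, has an estimate, SE, p-value, odds ratio and 95% CI. Table 121 has the same format.

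SAP section 12 records that this regression replaces the protocol's test, and gives as a reason that it has the merit of "providing the strength of the association between the treatment and probability of reporting any local or systemic event in terms of odds ratio". The replaced test was itself optional: in Protocol 11.6.2, "The proportion of subjects reporting symptoms may be compared between treatment arms using Chi-square" or Fisher's exact test.

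The primary safety objective in Protocol Table 1 is "To assess the safety and reactogenicity of 2018/2019 Fluzone and Flublok with and without AF03 or Advax-CpG55.2 adjuvant". For immunogenicity, the footnote to SAP Table 21 defines the GMT ratio as "the ratio of the GMT from the adjuvanted group divided by the GMT from the corresponding unadjuvanted group", so Groups 5 and 6 are compared there with Group 4.

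**The concern.** Three of the six arms are Flublok arms. For Fluzone, the tables give the adjuvant effect directly (2 vs 1 and 3 vs 1). For Flublok they do not: the rows for Groups 5 and 6 combine the difference between the two vaccines with the effect of the adjuvant.

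These two tables are the only planned between-arm comparison of solicited reactions, and the model was adopted for its odds ratios. A reader who takes a Flublok-plus-adjuvant row as the adjuvant effect is reading a different contrast. The layout also departs, without explanation, from the matched comparator used for the GMT ratios.

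**Working it through.** **What is printed.** Sorting the five odds ratios in each shell by what they estimate:

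| Row | Contrast | Meaning |
|---|---|---|
| Fluzone + AF03 | 2 vs 1 | adjuvant within Fluzone |
| Fluzone + Advax-CpG | 3 vs 1 | adjuvant within Fluzone |
| Flublok | 4 vs 1 | vaccine |
| Flublok + AF03 | 5 vs 1 | vaccine and adjuvant together |
| Flublok + Advax-CpG | 6 vs 1 | vaccine and adjuvant together |

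The other solicited-event outputs (Tables 117, 119, 122 and 123, Figures 96 and 97) are per-arm summaries. None gives 5 vs 4 or 6 vs 4.

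**How far the printed row can be from the within-Flublok effect.** The documents give no expected rates for these arms, so all counts below are assumptions, with the planned 40 subjects per arm. The six-arm model is saturated, so any contrast equals the two-arm log odds ratio, with SE = sqrt(1/a + 1/b + 1/c + 1/d).

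- Flublok 20/40, Flublok + AF03 32/40. Within Flublok: OR = (32/8)/(20/20) = 4.00. SE = sqrt(1/32 + 1/8 + 1/20 + 1/20) = 0.506. 95% CI 1.48 to 10.79, p = 0.006.
- The printed row (5 vs 1) for the same two Flublok arms depends on the Fluzone count:

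| Fluzone | Printed OR | Result |
|---|---|---|
| 16/40 | 4/(16/24) = 6.00 | p = 0.0004 |
| 20/40 | 4/(20/20) = 4.00 | p = 0.006 |
| 24/40 | 4/(24/16) = 2.67 | 95% CI 0.98 to 7.25, p = 0.055 |
| 28/40 | 4/(28/12) = 1.71 | p = 0.30 |

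**If the true Fluzone and Flublok rates are equal.** Then there is no systematic mismatch, but chance still separates arms 1 and 4. The ratio (printed OR)/(within-Flublok OR) equals odds(arm 4)/odds(arm 1), whatever happens in arm 5. Take the factor as the larger of this ratio and its inverse, and enumerate two independent Binomial(40, p) counts:

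| True rate in both arms | Median factor | Factor 1.5 or more | Factor 2 or more |
|---|---|---|---|
| 50% | 1.35 | 37% | 15% |
| 40% or 60% | 1.36 | 41% | 15% |

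**Can a reader rebuild 5 vs 4?** Yes, with care. Take Fluzone 24/40 and the Flublok arms above.

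- From the arm counts: 4.00 (1.48 to 10.79), exactly.
- From Table 120: the covariance of the two coefficients equals the intercept variance, so SE = sqrt(SE5² + SE4² − 2·SE_intercept²) = sqrt(0.2604 + 0.2042 − 2 × 0.1042) = 0.506. At 3 significant figures (the SAP section 10 convention) this gives 4.00 (1.48 to 10.77). At the one decimal drawn in the shell it gives 4.06 (1.34 to 12.3).
- Combining the two printed SEs as if independent is wrong: sqrt(0.2604 + 0.2042) = 0.682 instead of 0.506.

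**The case against.** The strongest reply is that nothing is wrong with the analysis. The model is saturated and the proposed change leaves the fit untouched. The trial tests no formal hypothesis. The safety outcome measures are occurrence of events by arm, whereas the adjuvanted-to-unadjuvanted GMT ratio is itself a named outcome, so the two need not share a comparator. Table 122 prints events and non-events for each arm, and it goes into the expedited report, so the two-by-two tables are available before Tables 120 and 121, which are marked for neither the expedited nor the topline report. The dashed row shows the reference in the usual way. The follow-on models are optional, and an overall treatment test does not depend on the reference arm. Protocol 2.3.1 says that for Flublok "local and systemic reactogenicity symptoms were generally similar in frequency and severity to those observed with the active control vaccines", which makes the wide gaps above unlikely.

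Most of this stands, and it limits the size of the point. The active controls in that sentence are not named as Fluzone, but similarity is the more plausible case, and the discrepancy is then sampling noise. A median factor of 1.35 is small beside a confidence interval whose limits differ by a factor of about 7.3 (10.79/1.48).

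What does not stand is the inference that the layout is as good as any other. The SAP chose to print odds ratios with intervals and p-values, and justified the model by them. Those that bear on the adjuvants are given for one vaccine and not for the other.

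**Conclusion.** The concern holds. The reference arm is read from the dashed row, since no sentence in the SAP names it. On that reading, neither within-Flublok adjuvant contrast is printed anywhere, and the two adjuvanted Flublok rows answer a mixed question. The contrasts can be recovered exactly from the arm counts, so this is a gap in presentation. It biases no estimate and loses no information.

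Its size depends on how far Fluzone and Flublok differ. In the assumed example, a within-Flublok odds ratio of 4.00 is shown as anything from 6.00 to 1.71. With equal true rates there is no systematic difference, and the two figures differ by a factor of 2 or more in about 15% of trials. It is an improvement worth making, but an optional one.

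**What to change.** Keep the six-arm model. Add one sentence to SAP 9.3.1 naming the contrasts of interest as 2 vs 1, 3 vs 1, 5 vs 4 and 6 vs 4. Add lines for them, each with odds ratio and 95% CI, to the shells of Tables 120 and 121. Use the same contrasts in any single-symptom models that follow. The Flublok vs Fluzone row can stay as the vaccine comparison. If the p-value column is kept, it can be filled for the new lines too.

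The cost is that sentence and a few lines in two shells. All results come from the model already planned, and no new data are needed.
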